## **9.9 LIMITATIONS OF THE RESEARCH METHODS**

This study will be conducted using data from insurance claims and is subject to certain limitations. One limitation is that these are based on a large, non-random convenience sample, which may contain biases or lack generalizability to other populations. Data also come mostly from large employers, and although the database also includes a large amount of data from health plans, data from medium and small firms may be underrepresented.

Additionally, the MarketScan database also poses some limitations inherent to administrative claims data. Electronic outpatient pharmacy dispensing records are considered accurate because pharmacists fill prescriptions with little room for interpretation and are reimbursed by insurers on the basis of detailed, complete, and accurate claims submitted electronically (Sternbach 1988, Levy 2003). Pharmacy dispensing information is usually seen as the gold standard of drug exposure information compared to self-reported information (West 1995) or prescribing records in outpatient medical records (West 1994). However, drugs used during hospital stays are not recorded in this data source. Claims data are subject to certain limitations. The presence of a claim for a filled prescription does not indicate that the medication was consumed or that it was taken as prescribed, and any medications filled over-the-counter or provided as samples by the physician will not be observed in the claims data. Furthermore, as with all claims-based analyses, study results may not be generalizable to the overall population as patients who have commercial health insurance may be different from those with non-commercial or without (commercial) health insurance. Finally, patients are required not to have a claim for Olodaterol/Tiotropium Bromide or Umeclidinium/Vilanterol during the baseline period, but use of these medications may have occurred prior to the start of the baseline period.

In the analytical portion of this protocol, propensity score matching will be used to estimate relative persistence between the two exposures of interest. Various covariates are included in the prediction model of the propensity scores, but as with all non-interventional studies, the potential for unmeasured and residual confounding cannot be ruled out.

## **9.10 OTHER ASPECTS**

Not applicable.

## **9.11 SUBJECTS**

### **9.11.1 Cases**

See [Section 9.2.2](#).

## 9.11.2 Controls

Not applicable.

## 9.12 BIAS

In principle, electronic outpatient pharmacy dispensing records are considered accurate because pharmacists fill prescriptions with little room for interpretation, and are reimbursed by insurers based on detailed, complete, and accurate claims submitted electronically (**Levy 2003; Stergachis 1988**). Pharmacy dispensing information is usually seen as the gold standard of drug exposure information compared to self-reported information or prescribing records in outpatient medical records.

The population-based nature of the database will avoid selection bias and ensure external validity. Confounding bias through observable covariates will be controlled for by the design, which includes propensity score matching.

To minimize misclassification of the recorded patient characteristics, previously validated algorithms or code lists will be used whenever available. Code lists will be reviewed by the qualified medical reviewers prior to implementation. Basic plausibility checks will be implemented for continuous variables (e.g. age, etc.).

While this analysis is designed to assess non-persistence as an endpoint. Whether or not the patient actually complied with the prescription cannot be known. For example, a patient may fill a 30-day prescription, but may only comply with the medication for a few days before truly discontinuing, leading to an overestimation of persistence when using claims data. Furthermore, even if a patient did comply, they may administer the doses incorrectly.

The covariates chosen in [section 9.3.3](#). are hypothesized to be confounders in the relationship between exposure and outcome. The range and quantity of variables selected are aimed to make the two exposure groups more comparable so that the interpretation of effect estimates may be more meaningful.

## 10. PROTECTION OF HUMAN SUBJECTS

As the present study is a non-interventional retrospective cohort study, the most significant potential impact on the participants would be the potential for individual identification and loss of privacy. Patients in the MarketScan dataset are de-identified, such that names are not linked to patient IDs. Thus, the risks to participants are expected to be minimal.

## **11. MANAGEMENT AND REPORTING OF ADVERSE EVENTS/ADVERSE REACTIONS**

Data is anonymized and extracted, analyzed, validated and reported in aggregate.

There is no potential that any employee of BI or agent working on behalf of BI will access individual patient data in which the patient may be identified during data compilation, data reporting or data analysis.

Based on current guidelines from the International Society for Pharmacoepidemiology [[R11-4318](#)] and the EMA [[R13-1970](#)], non-interventional studies such as the one described in this protocol, conducted using health care records, do not require expedited reporting of suspected adverse events/reactions. Specifically, as stated in section VI.C.1.2.1 of Guideline on Good Pharmacovigilance Practices (GVP), Module VI – Management and Reporting of Adverse Reactions to Medicinal Products, for non-interventional study designs, which are based on use of secondary data, reporting of adverse reactions is not required.

## **12. PLANS FOR DISSEMINATING AND COMMUNICATING STUDY RESULTS**

The results of the study will primarily serve internal decision making for future studies on comparative effectiveness. These baseline results will be published as an abstract and/or manuscript. Conference and Journal to be decided.

### **13.2 UNPUBLISHED REFERENCES**

Not Applicable

**ANNEX 1. LIST OF STAND-ALONE DOCUMENTS**

Number	Document Reference Number	Date	Title
1	Annex 1	19 April 2019	List of stand-alone documents
2	Annex 2	19 April 2019	ENCEPP Checklist for study protocols
3	Annex 3	19 April 2019	List of medication measure definitions
4	Annex 4	19 April 2019	List of comorbidity and other measure definitions
5	Annex 5	19 April 2019	Table shells and proposed figures

**ANNEX 2. ENCEPP CHECKLIST FOR STUDY PROTOCOLS**

Not Applicable

### ANNEX 3. LIST OF MEDICATION MEASURE DEFINITIONS

Name	Components
Corticosteroids	Betamethasone, *beclometasone (beclomethasone), cortisone acetate, dexamethasone, hydrocortisone, methylprednisolone, prednisolone, prednisone, triamcinolone, deflazacort, fludrocortisone
Short Acting Beta Agonist	Albuterol, metaproterenol, levalbuterol, pirbuterol, terbutaline
Short Acting Muscarinic Antagonist	Ipratropium
Long Acting Muscarinic Antagonist (LAMA)	Umeclidinium, glycopyrrolate, tiotropium, aclidinium, Incruse, Seebri, Spiriva, Tudorza
Long Acting Beta Agonist (LABA)	Indacaterol, arformoterol, formoterol, salmeterol, olodaterol, Arcapta, Atimos, Brovana, Perforomist, Serevent, Striverdi, Foradil
Inhaled Corticosteroids	Flunisolide, budesonide, mometasone, ciclesonide, fluticasone, beclomethasone, Aerobid, Aerospan, Alvesco, Armonair, Arnuity, Asmanex, Azmacort, Flixotide, Flovent, Pulmicort, Qvar
LAMA / LABA combination	indacaterol/glycopyrrolate, glycopyrrolate/formoterol, Utibron, Bevespi
LABA / ICS combination	Fluticasone/vilanterol, budesonide/formoterol, fluticasone/salmeterol, mometasone/formoterol, Advair, Symbicort, Breo, Dulera
LAMA / LABA / ICS combination	Fluticasone/umeclidinium/vilanterol, Trelegy
NSAIDs	Phenylbutazone, sulindac, tolmetin, diclofenac, etodolac, ketorolac, piroxicam, meloxicam, ibuprofen, naproxen, ketoprofen, fenoprofen, suprofen, flurbiprofen, oxaprozin, mefanamic acid, meclofenamic acid, celecoxib, rofecoxib, valdecoxib, nabumetone, glucosamine sulfate

Opioids	Morphine, hydromorphone, oxycodone, dihydrocodeine, fentanyl, pentazocine, buprenorphine, butorphanol, nalbuphine, tramadol, tapentadol, hydrocodone, codeine
Antihistamines/Antiallergic s	Diphenhydramine, clemastine, carboxamine, doxylamine, brompheniramine, dexchlorpheniramine, pheniramine, tripeptenamine, promethazine, thiethylperazine, cyclizine, chlorcyclizine, cetirizine, cyproheptadine, phenindamine, triprolidine, azatadine, astemizole, terfenadine, loratadine, ketotifen, azelastine, levocabastine, epinastine, fexofenadine, desloratadine, ephedrine, phenylephrine, oxymetazoline, xylometazoline, naphazoline, nedocromil
Oral Antibiotics	Demeclocycline, doxycycline, chlortetracycline, oxytetracycline, tetracycline, minocycline, tigecycline, chloramphenicol, ampicillin, carbenicillin, amoxicillin, bacampicillin, mezlocillin, piperacillin, ticarcillin, dicloxacillin, cloxacillin, oxacillin, flucloxacillin, nafcillin, sulbactam, tazobactam, cefazolin, cefadroxil, cefoxitin, cefuroxime, cefamandole, cefaclor, cefotetan, loracarbef, cefprozil, cefotaxime, ceftazidime, ceftriaxone, ceftizoxime, cefixime, cefoperazone, cefpodoxime, ceftibuten, cefdinir, cefditoren, cefepime, aztreonam, meropenem, ertapenem, doripenem, trimethoprim, sulfapyridine, sulfanilamide, sulfathiazole, sulfamethoxazole, sulfadiazine, sulfamerazine, sulfapyridine, sulfanilamide, sulfathiazole, sulfadiazine, sulfamethoxazole, sulfachlorpyridazine, sulfamerazine, sulfacetamide, erythromycin, troleandomycin, clarithromycin, azithromycin, dirithromycin, telithromycin, clindamycin, lincomycin, quinupristin/dalfopristin, streptomycin, tobramycin, gentamicin, kanamycin, neomycin, amikacin, netilmicin, paromomycin, ofloxacin, ciprofloxacin, enoxacin, norfloxacin, lomefloxacin, sparfloxacin, grepafloxacin, levofloxacin, trovafloxacin, moxifloxacin, gemifloxacin, gatifloxacin, delafloxacin, cinoxacin, vancomycin, telavancin, dalbavancin, oritavancin, colistin, polymyxin b, metronidazole, tinidazole, nitrofurantoin, fosfomycin, spectinomycin, methenamine, mandelic acid, linezolid, daptomycin, bacitracin, tedizolid, novobiocin
Diabetes Mellitus Medications	Sulfonylureas (chlorpropamide, tolbutamide, tolazamide, glipizide, gliclazide, acetohexamide), biguanides (metformin), thiazolidinediones (troglitazone, rosiglitazone, pioglitazone), alpha-glucosidase inhibitors (acarbose, miglitol), meglitinides (repaglinide, nateglinide, mitiglinide), DPP-4 inhibitors (sitagliptin, vildagliptin, saxagliptin, alogliptin, linagliptin), GLP-1 receptor agonists (exenatide, liraglutide, lixisenatide, albiglutide, dulaglutide, semaglutide), SGLT-2 inhibitors (dapagliflozin, canagliflozin, empagliflozin)
Insulin	Rapid-acting insulin, short-acting insulin, intermediate-acting insulin, long-acting insulin
Methotrexate	Methotrexate
Anticoagulants	Vitamin K antagonists (phenindione, warfarin), heparins (heparin, antithrombin III, dalteparin, enoxaparin, danaparoid, tinzaparin), platelet aggregation inhibitors (clopidogrel, ticlopidine, dipyridamole, epoprostenol, iloprost, abciximab, eptifibatide, tirofiban, treprostil, prasugrel, cilostazol, ticagrelor, cangrelor, vorapaxar, seleipipag), direct thrombin

	inhibitors (desirudin, lepirudin, argatroban, bivalirudin, dabigatran etexilate), direct factor Xa inhibitors (rivaroxaban, apixaban, edoxaban), anticoagulant enzymes (anistreplase, urokinase, reteplase, drotrecogin alfa, tenecteplase), defibrotide, fondaparinux
Statins	Atorvastatin, fluvastatin, lovastatin, pravastatin, rosuvastatin, simvastatin, pitavastatin, cerivastatin
Antihypertensives	Angiotensin converting enzyme (ACE) inhibitors, angiotensin receptor blockers, beta-blockers, calcium channel blockers, diuretics, alpha-blockers, alpha-beta blockers, vasodilators
Anti-psychotics/ Anti-depressives/Anxiolytics	Desipramine, clomipramine, trimipramine, amitriptyline, nortriptyline, protriptyline, doxepin, amoxapine, maprotiline, fluoxetine, citalopram, paroxetine, sertraline, fluvoxamine, escitalopram, isocarboxazid, phenelzine, tranylcypromine, tryptophan, trazodone, nefazodone, minaprine, mirtazapine, bupropion, venlafaxine, milnacipran, duloxetine, desvenlafaxine, vilazodone, vortioxetine, selegiline, chlorpromazine, promazine, acepromazine, triflupromazine, fluphenazine, perphenazine, prochlorperazine, trifluoperazine, thioridazine, mesoridazine, pipotiazine, haloperidol, droperidol, molindone, ziprasidone, lurasidone, thiothixene, pimozide, loxapine, clozapine, olanzapine, quetiapine, asenapine, lithium, risperidone, aripiprazole, paliperidone, iloperidone, cariprazine, brexpiprazole, pimavanserin, diazepam, chlordiazepoxide, oxazepam, lorazepam, clobazam, alprazolam, halazepam, hydroxyzine, meprobamate, buspirone
Oxygen Therapy	Oxygen

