#### **9.3.3 Covariates**

Covariates will be identified based on data recorded within 180 days prior to or on the index date (date of dispensing/initiation of the exposure), unless otherwise specified. If multiple measurements are made in the baseline period, then the most recent measurement will be used.

Covariates will be used to predict propensity scores in later analyses. Absolute and relative frequencies of each covariate will also be reported in Table Shells 1 and 2 (see [Annex 5](#)). Detailed descriptions of the listed covariates can be found in [Annex 3](#) and [4](#).

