#### **Concomitant Medications**

- Oral Corticosteroids
- Short acting muscarinic antagonist (SAMA)
- Short acting beta agonist (SABA)
- Long acting muscarinic antagonist (LAMA)
- Long acting beta agonist (LABA)
- Inhaled corticosteroid (ICS)
- LAMA / LABA combination (that is not Stiolto or Anoro)
- LABA / ICS combination
- LAMA / LABA / ICS combination
- NSAIDs
- Antihistamines
- Opioids
- Oral antibiotics
- Antidiabetic Agents (not including insulin)

- Insulin (basal or mealtime)
- Methotrexate
- Statins
- Antihypertensives
- Anticoagulants
- Anti-psychotic/anti-depressives/anxiolytic
- Oxygen therapy

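### Annex 3 lists the ingredients behind the oral steroid, inhaled steroid and oral antibiotic covariates without a route or dose-form rule, so the flags may capture other products

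*Combined protocol and SAP*

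**What the plan says.** The Concomitant Medications list in section 9.3.3 includes "Oral Corticosteroids", inhaled corticosteroids and oral antibiotics. For the operational definitions the section points elsewhere: "Detailed descriptions of the listed covariates can be found in" Annexes 3 and 4.

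Annex 3 has two columns, a measure name and its components. The relevant rows are:

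- **Corticosteroids.** The heading omits the word oral. The row opens with betamethasone and beclomethasone and continues "cortisone acetate, dexamethasone, hydrocortisone, methylprednisolone, prednisolone, prednisone, triamcinolone, deflazacort, fludrocortisone".
- **Inhaled Corticosteroids.** "Flunisolide, budesonide, mometasone, ciclesonide, fluticasone, beclomethasone, Aerobid, Aerospan, Alvesco, Armonair, Arnuity, Asmanex, Azmacort, Flixotide, Flovent, Pulmicort, Qvar". Six bare ingredients stand next to eleven brand names.
- **Oral Antibiotics.** A long ingredient list that includes "cefepime, aztreonam, meropenem, ertapenem, doripenem", "streptomycin, tobramycin, gentamicin, kanamycin, neomycin, amikacin" and "linezolid, daptomycin, bacitracin, tedizolid, novobiocin".

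None of the three rows restricts route, dose form or drug code. Under section 9.7.1.1, any occurrence in the 180-day baseline sets a medication covariate to yes. Section 9.2.2 (Matched Cohort) puts all covariates except the Charlson components into the propensity score, and section 9.7.1.3 uses the same set in the adjusted models.

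**The concern.** In claims data, oral steroid and antibiotic fills are the usual traces of a recent exacerbation, and inhaled steroid use marks background therapy. The covariate list has no lung-function values, only whether tests were done, so treatment markers carry much of the severity information. The matched Cox model in section 9.7.1.3 has treatment as its only term, so its confounding control rests on the score.

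Several listed ingredients also exist in other forms. This is general drug knowledge, not something the documents state. Hydrocortisone, triamcinolone and betamethasone are dispensed as creams or injections; fluticasone, mometasone and budesonide as nasal sprays. Meropenem, ertapenem and daptomycin are injected, and bacitracin is largely topical. Matched on name alone, a prescribed hydrocortisone cream would set the oral steroid flag and a prescribed nasal fluticasone would set the inhaled flag. Table 2 in Annex 5 would still label the first of these as oral use, and a small standardized difference on the flag could be read as balance on exacerbation history.

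**Working it through.** The documents attach no figure to this point, so there is none to reproduce. The check is a comparison of text, followed by an illustration on assumed inputs.

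**Text.**

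1. Comparing the steroid rows: Corticosteroids has 11 ingredients; Inhaled Corticosteroids has 6 ingredients and 11 brands. Beclomethasone is in both, so as written one beclomethasone record sets both the oral and the inhaled flag. This needs no outside knowledge.
2. The injected and topical agents under Oral Antibiotics show that the heading did not limit what was listed beneath it.
3. No other section supplies a route rule. Section 9.3.1 identifies the two exposures by generic and brand name, and the dementia measure in Annex 4 also matches on generic name. Neither statement governs these three covariates, but they are the drug-matching methods the plan does describe. Diagnosis measures in Annex 4 specify claim setting, code position and spacing, so the plan elsewhere works at this level of detail.

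**Illustration.** All inputs are assumed: true oral steroid use p1 = 0.38 in the Olodaterol/Tiotropium arm and p0 = 0.33 in the comparator; every true user is flagged (sensitivity 1); a share f of true non-users is flagged through another form, equal in both arms.

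- Flag prevalence in an arm: F = p + (1 - p)f.
- True users among the flagged: PPV = p/F.
- Matching gives the comparator the flag prevalence F1, so its true use becomes F1 × PPV0.
- Remaining imbalance: p1 - F1 × PPV0. Its share of the starting difference: divide by 0.05.

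| f | F1 | F0 | PPV0 | F1 × PPV0 | Remaining imbalance | Share of 0.05 |
|---|---|---|---|---|---|---|
| 0.10 | 0.442 | 0.397 | 0.831 | 0.3674 | 0.0126 | 0.252 |
| 0.15 | 0.473 | 0.4305 | 0.767 | 0.3626 | 0.0174 | 0.348 |
| 0.20 | 0.504 | 0.464 | 0.711 | 0.3584 | 0.0216 | 0.431 |

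In absolute terms, 1.3, 1.7 or 2.2 percentage points remain of an assumed difference of 5.

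**Translation to a ratio.** If oral steroid use multiplied discontinuation by R (also assumed), the bias factor is [1 + 0.38(R - 1)] / [1 + F1 × PPV0 × (R - 1)].

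| f | R = 1.2 | R = 1.5 | R = 2.0 |
|---|---|---|---|
| 0.10 | 1.002 | 1.005 | 1.009 |
| 0.20 | 1.004 | 1.009 | 1.016 |

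For example, at f = 0.20 and R = 2.0: 1.38/1.3584 = 1.016.

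**Unequal false flags.** Suppose instead that true use is 30% in one arm and the flag is exactly balanced, but f differs by arm. At f of 5% v 10%, the common flag prevalence is 0.30 + 0.70 × 0.05 = 0.335, and true use in the other arm is (0.335 - 0.10)/0.90 = 0.261, a standardized difference of 0.09. At 5% v 20% it is (0.335 - 0.20)/0.80 = 0.169, a standardized difference of 0.31. Nothing in the documents indicates that f differs between arms.

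**The case against.** The strongest reply is that Annex 3 is not executable code. Antihypertensives appear as drug classes, insulin by duration of action, and oxygen as a single word, so all of it must be translated into codes. Section 9.12 plans medical review of code lists before use; section 9.8 plans clinical input and a second-analyst check, and lets measure definitions be modified. A programmer could add a route filter at that step. This stands in part: that other-route products will in fact be counted is an inference, not something the plan says. But no filter is stated, and section 9.8 also requires changes to the protocol to be documented as amendments, so an unrecorded filter would not be the documented definition.

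A reader might infer that all three covariates lack any route. The documents do not support that. Two of the three rows carry the route in their heading, and the steroid covariate is called oral in the Abstract, in section 9.3.3 and in Tables 2 and 3. The missing word in Annex 3 may be a label slip. It does not explain the beclomethasone overlap or the injected antibiotics. The beclomethasone entry in the Corticosteroids row carries an asterisk with no footnote in the text available to me; if one exists and limits the form, the overlap may already be settled.

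The size is also open to challenge. Section 9.9 says over-the-counter products are not observed, which removes creams and nasal sprays bought that way, and clinic-administered injections may rarely appear as drug records. The score also contains short-acting bronchodilators, LABA/ICS, oxygen, respiratory hospitalization, emergency visits, pneumonia and lower respiratory infection, and matching on these would probably remove part of the residual. These points stand.

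**Conclusion.** The point holds as an over-inclusive stated definition. The steroid row gives no route at all, and the other two rows name a route that their components do not follow. If the lists are applied by ingredient name as written, the three flags mix in other-route products, which weakens severity control and mislabels Table 2.

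A reader might take the 25-43% share in the table above as the size of the problem. It is a share of a small assumed difference, treats the flag as the only covariate, and rests on false-flag rates with no source in the documents. The absolute figure is the fairer one: about 1.3-2.2 percentage points of imbalance in true oral use, probably less given the correlated covariates, and a ratio bias of at most about 1.6% even if oral steroid use doubled discontinuation. That holds only for equal false-flag shares; unequal shares could leave more. No inputs are available for inhaled steroids or antibiotics, so these figures should not be carried over to them.

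Nor do the documents support saying that the primary hazard ratio is biased in a particular direction or by a known amount. The case for acting is that the definition is wrong as written and cheap to correct.

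**What to change.** In Annex 3:

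1. Rename the first row Oral Corticosteroids, to match section 9.3.3 and Tables 2 and 3.
2. Restrict the corticosteroid and antibiotic rows to oral dose forms, and the inhaled corticosteroid row to orally inhaled (not nasal) forms, at drug-code level.
3. Remove the beclomethasone overlap between the two steroid rows.
4. State that these restrictions apply before the propensity score is fitted, and record the change as section 9.8 requires.

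The cost is a form filter and a rerun of three covariates, followed by the score and the tables that depend on it. Exposure and outcome definitions do not change, and no new data should be needed.

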## Protocol for non-interventional studies based on existing data

Document Number:	c30445781-01
BI Study Number:	1237-0090
BI Investigational Product(s):	Stiolto® Respimat®
Title:	The Role of Inhaler Device in the Treatment Persistence with Dual Bronchodilators in Patients with COPD
Protocol version identifier:	1.0
Date of last version of protocol:	N/A
PASS:	No
EU PAS register number:	Study not registered
Active substance:	Olodaterol and Tiotropium Bromide (ATC R03AL06) Umeclidinium and Vilanterol (ATC R03AL03)
Medicinal product:	Stiolto® Respimat®; Anoro® Ellipta®
Product reference:	N/A
Procedure number:	N/A
Joint PASS:	No
Research question and objectives:	
The primary objective of the study is to use US data to determine relative persistence between Olodaterol/Tiotropium Bromide delivered with the Respimat soft mist inhaler and Umeclidinium/Vilanterol delivered with the Ellipta dry powder inhaler using a 1:2 propensity score matched analysis.
 
The secondary objectives of the study are as follows:
 
 
- Characterize new users of Olodaterol/Tiotropium Bromide and Umeclidinium/Vilanterol in terms of demographics, medication use, comorbidities, and other variables, before and after propensity score matching.
 
- Determine the incidence rate and proportion of patients discontinuing or switching among new users of Olodaterol/Tiotropium Bromide and Umeclidinium/Vilanterol.
 
- Determine the relative rate and proportion of patients discontinuing between Olodaterol/ Tiotropium Bromide and
 

	Umeclidinium/Vilanterol. using a standard multivariate analysis (If feasible).
Country(-ies) of study:	United States
	T: Email:
Author:	T: Email:
	BI contact person:
Marketing authorisation holder(s):	
MAH contact person:	
In case of PASS, add:	N/A
In case of PASS, add:	N/A
Date:	22 November 2019
Page 1 of 69	
Proprietary confidential information © 2019 Boehringer Ingelheim International GmbH or one or more of its affiliated companies. All rights reserved. This document may not - in full or in part - be passed on, reproduced, published or otherwise used without prior written permission	

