## 7. RATIONALE AND BACKGROUND

Chronic obstructive pulmonary disease (COPD) is a common disease characterized by airway obstruction confirmed by spirometry, often including small airway obstruction, chronic bronchitis and emphysema (**Barnes 2015**). No known medications can reverse COPD, but regular maintenance treatments can help manage symptoms, reduce frequency of COPD exacerbations and improve health-related quality of life. Inhaled therapies are the cornerstone of COPD disease management approaches. The aim of inhaled therapy is to deliver agents directly to the lungs, thereby offering benefits while minimizing the potential for treatment-related adverse effects (**Braido 2016**).

Adherence to obstructive lung disease therapies involves patients initiating their prescribed therapy, implementing it as prescribed (i.e. correctly administering the prescribed dose at the physician directed frequency), and persisting with treatment (**Braido 2016; Mäkelä 2013**). Central to the therapeutic benefit of inhaled therapies is their successful administration which requires patients to have knowledge and understanding of (and ability to implement) the appropriate inhaler technique required to optimize both the dispensed and administered doses (**Braido 2016**). Inspiratory capabilities of patients with COPD are affected by increasing static and dynamic hyperinflation and weakening of the respiratory muscles, causing many patients to have peak inspiratory flow rates that are suboptimal to use many dry-powder inhalers (DPIs) (**Sohini 2017**). This paradoxical situation may lead to improper inhalation that prevents successful drug delivery to the lungs, which may affect treatment effectiveness. On the other hand, soft mist inhalers (SMI) force a metered dose of drug solution through a precise nozzle to deliver consistent and reliable doses to the lungs with each actuation (**Dalby 2004**) and may help preserve benefits in patients with diminished peak inspiratory flow rates.

Stiolto® Respimat®, a combination of Olodaterol and Tiotropium Bromide delivered via soft mist inhaler (SMI), was approved in May 2015 in the US and July 2015 in the EU (marketed

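### The LAMA covariate pools tiotropium (in Stiolto) with umeclidinium (in Anoro), so matching can look balanced while prior use of the index ingredients is not

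*Combined protocol and SAP*

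**What the plan says.** The title page gives the index products as olodaterol with tiotropium (Stiolto) and umeclidinium with vilanterol (Anoro). Section 9.3.3 lists prior respiratory drugs by class, and Annex 3 defines five maintenance bronchodilator classes:

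- LAMA: "Umeclidinium, glycopyrrolate, tiotropium, aclidinium, Incruse, Seebri, Spiriva, Tudorza"
- LABA: "Indacaterol, arformoterol, formoterol, salmeterol, olodaterol, Arcapta, Atimos, Brovana, Perforomist, Serevent, Striverdi, Foradil"
- LAMA/LABA: "indacaterol/glycopyrrolate, glycopyrrolate/formoterol, Utibron, Bevespi"
- LABA/ICS: "Fluticasone/vilanterol, budesonide/formoterol, fluticasone/salmeterol, mometasone/formoterol, Advair, Symbicort, Breo, Dulera"
- LAMA/LABA/ICS: "Fluticasone/umeclidinium/vilanterol, Trelegy"

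Section 9.7.1.1 codes each medication as ever or never used in the 180-day baseline. Section 9.2.2 (Matched Cohort) puts all the section 9.3.3 covariates, except the Charlson components, into the propensity score. Among prior drugs, section 9.2.2 excludes only the two fixed-dose study products. In section 9.7.1.3 the matched Cox model contains treatment alone, and the multivariable models use the same class-level covariates. Tables 2 and 3 in Annex 5 have one row per class. None of the four sensitivity analyses in section 9.7.2 concerns the prior product.

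**The concern.** A patient who was taking tiotropium and starts Stiolto continues one ingredient and adds another. A patient who was taking umeclidinium and starts Stiolto changes LAMA. The plan gives both the same value, LAMA yes. If prescribers tend to stay with the ingredient a patient already has, prior ingredient predicts product choice. If patients who already take an ingredient stop more or less often, it also predicts the outcome. It would then be a confounder that is visible in the dispensing data but lost in the coding.

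The diagnostics would not reveal it. A standardised difference near zero on the LAMA row is compatible with quite different tiotropium and umeclidinium shares in the two arms. Section 9.12 relies on the matched design to control confounding through observable covariates, so this gap bears on the primary hazard ratio.

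**Working it through.** **The plan's own figure.** Section 9.5 gives 3,889 Stiolto and 10,862 Anoro initiators: 3,889 + 10,862 = 14,751, as stated. A full 1:2 match would be 3,889 to 7,778. The plan states no event rate, effect size or prior-product share.

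**Class check.** Each Annex 3 class set against the four index ingredients:

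| Class | Stiolto ingredient | Anoro ingredient | Consequence |
|---|---|---|---|
| LAMA | tiotropium | umeclidinium | both products pooled |
| LABA | olodaterol | none | mixed with four unrelated drugs |
| LAMA/LABA | none | none | no problem |
| LABA/ICS | none | vilanterol | mixed with three unrelated combinations |
| LAMA/LABA/ICS | none | umeclidinium and vilanterol | single product, can be balanced as defined |

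One class of five pools ingredients of both products, and two mix one product's ingredient with other drugs.

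**Size of confounding (all inputs assumed).** Let q be the prevalence of prior LAMA use, equal in both arms after matching. Let s1 and s0 be the tiotropium share of prior LAMA users in the Stiolto and Anoro arms, and g the discontinuation hazard ratio for prior tiotropium users against other patients. The matched hazard ratio is multiplied by about

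[1 + q·s1·(g − 1)] / [1 + q·s0·(g − 1)].

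- q = 0.4, s1 = 0.95, s0 = 0.5, g = 0.7: (1 − 0.114)/(1 − 0.060) = 0.886/0.940 = 0.943
- q = 0.2, s1 = 0.9, s0 = 0.7, g = 0.9: (1 − 0.018)/(1 − 0.014) = 0.982/0.986 = 0.996
- s1 = s0: exactly 1.00

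The factor exceeds 1 if g is above 1 or if the shares are reversed.

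**Precision for comparison.** With a proportion p discontinuing in a full match, SE(log HR) = √[1/(3,889p) + 1/(7,778p)]. At p = 0.5 this is 0.0278, and exp(1.96 × 0.0278) = 1.056. At p = 0.8 it is 0.0220, giving 1.044. On the log scale the most extreme factor, ln 0.943 = −0.059, compares with half-widths of 0.054 and 0.043. That is 1.1 to 1.4 half-widths at the corner of the range, and less elsewhere.

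**Simulated matching.** 14,751 patients, 1:2 greedy matching, caliper 0.05, 20 runs per scenario, no true product effect, Monte Carlo error about 0.005. Assumed inputs: 35% prior LAMA use, 80% of it tiotropium, prior product predicting choice.

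- Balance with pooled LAMA: class standardised difference 0.00, tiotropium +0.20, umeclidinium −0.39.
- Balance with LAMA split by ingredient: both about 0.01 or less. Matched Stiolto patients fall from about 3,670 to 3,440, or 6%.
- Prior tiotropium itself multiplies the hazard by 0.80 or 1.25: HR 0.986 or 1.020 pooled, 0.997 or 1.005 split. With no history effect the two approaches gave 0.992 and 1.000, so the smaller shifts are close to simulation noise.
- The effect belongs instead to stepping up within the same family: at 0.80, HR 0.943 pooled and 0.924 split; at 1.25, 1.066 and 1.085. Splitting does not remove this effect; here the HR moved further from 1.

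The last result is expected. A prior tiotropium user is a same-family patient in the Stiolto arm and a cross-family patient in the Anoro arm. Balancing prior tiotropium leaves that contrast in place, because it is an interaction of prior product with treatment.

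**The case against.** Prior treatment by class is already in the score, the covariate list is long, and section 9.9 concedes residual confounding. The documents contain nothing on how many patients step up from an ingredient, or on whether they persist longer. In the simulation, confounding by prior tiotropium alone moved the hazard ratio to 0.986 or 1.020, about 0.6 to 0.8 of a standard error (0.0235 at 70% events). These points stand as limits on the size. They do not answer the coding problem: section 9.9 does not mention prior product, and neither the balance tables nor the multivariable model can detect it.

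Stronger readings are tempting but unsupported:

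- A reader might infer that all the LAMA, LABA and combination covariates merge the two product families. Only LAMA does.
- A reader might take same-family step-up as an established driver of both choice and persistence, and attach a large bias to it. The documents give no shares or hazards, and that effect is not ordinary confounding that better covariates would remove.
- A reader might add familiarity with the inhaler. Annex 3 assigns no device to any prior product. The rationale in section 7, "Central to the therapeutic benefit of inhaled therapies is their successful administration which requires patients to have knowledge and understanding", concerns technique and therapeutic benefit; it does not address prior ingredients or product choice.

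**Conclusion.** The point holds as a gap in confounder control and in balance reporting, centred on LAMA and present to a lesser degree for olodaterol and vilanterol. Following the plan could show balance at class level while prior use of the index ingredients differs between matched arms. Whether it does, and in which direction, cannot be told from the documents. Under the assumed inputs the effect runs from negligible to about one 95% CI half-width, and it is nil if the ingredient mix is equal across arms. The conclusion rests on prior ingredient affecting both choice and persistence, which is plausible but not shown. The plan should be changed on this point before analysis; the gap does not by itself invalidate the design.

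**What to change.** In section 9.3.3 and Annex 3, keep the existing class flags and add baseline indicators for tiotropium, umeclidinium, olodaterol and fluticasone/vilanterol. Include them in the propensity score and in the multivariable models of section 9.7.1.3, and give each a row in Tables 2 and 3. The new flags should not replace the classes, and the remaining drugs should not be merged into one group: either would lose distinctions that the plan now makes. The triple combination keeps its own flag.

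In section 9.7.2, add one sensitivity analysis of the matched hazard ratio in patients with no baseline dispensing of any of the four index ingredients, counting the triple combination as exposure. Stratifying by prior component use is an alternative. This analysis is needed as well as the indicators, because they cannot remove a prior-product-by-treatment effect.

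The drug names are already in Annex 3, so the work is four indicators and one further analysis. The price is somewhat fewer matched patients (about 6% in the simulation, which split LAMA only) and a smaller sample, with wider intervals, in the restricted analysis.
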